## 12 Endpoints of clinical investigation

### 12.1 Generalized linear mixed model

Within the study, the primary endpoint will be analysed using the generalized linear mixed model.

The general form of the model is given by:

$$y = \beta_0 + X\beta + Z\gamma$$

where  $y$  Model-specific, individually estimated value vector (change from baseline in IELT),  $X$  is here a matrix of the expression of the corresponding variable for treatment and period,  $\beta_0$  is a vector containing the fixed intercept and  $\beta$  is a matrix of fixed effects regression coefficient respectively;  $\gamma$  is a matrix of the random effects for each subject.  $Z$  is a design matrix that links the respective random effect with the correct indiciduum. The covariance of the random effect will be modelled using a compound symmetry. If this model doesn't fit, an unstructured covariance can be used instead.

Generalized linear mixed models can be seen as a special cases hierarchical generalized linear model, in which the random effects (subjects) are normally distributed.

### 12.2 Statistical hypotheses for primary endpoint

The differences between the 5% benzocaine condom with the standard NRL condom will be presented with a 95% CI and an associated p-value. If the GLMM can't handle the violation, then in the worst-case scenario a non-parametric test such as Wilcoxon signed ranks test will be applied.

Therefore, first we consider the null hypothesis under investigation as

$H_0$ : The beta coefficient  $\beta_1$  of the regression for the group difference from A to Control is equal to 0.

which is tested against the alternative hypothesis.

$H_1$ : The beta coefficient  $\beta_1$  of the regression for the group difference from A to Control is not equal to 0.

These hypotheses are expressed mathematically by

$$H_0: \beta_1 = 0$$

$$H_1: \beta_1 \neq 0$$

where  $\beta_1$  is the regression coefficient of IELT after 4 weeks.

### 12.3 Secondary endpoints

In the event of any protocol deviations that warrant exclusion from the FAS, an analysis of the primary endpoint based on the PP population will be performed.

Statistical testing	
The change from baseline in IELT will be analysed using a linear mixed model using data from all three condom groups, with the primary comparison between the 5% benzocaine condom with the standard NRL condom.
 
The test is carried out separately for all three condom groups. This analysis is carried out in the FAS population. The analysis is repeated as a sensitivity analysis in the PP population.
 
Analysis of Event-level Male Sexual (EMSEX) pleasure scale is based on a raw data comparison to the baseline of standard NRL condom by GLMM. The test is carried out separately for all three condom groups.
 
Analysis of the proportion values of IELT increasement is based on the proportion of subjects who achieve an increase of 2 minutes on the IELT comparison to the baseline of standard NRL condom by GLMM.
 
Analysis of the proportion values of IELT increasement is based on the proportion of subjects who achieve an increase of 3 minutes on the IELT comparison to the baseline of standard NRL condom by GLMM.
 
Analysis of the proportion values of IELT increasement is based on the proportion of subjects who achieve an increase of 4 minutes on the IELT comparison to the baseline of standard NRL condom by GLMM.

---------------------	--

Descriptive analysis	
A descriptive analysis is performed for each of the secondary endpoints separately for each condom group.
 
The descriptive analysis of the IELT with the Test Condom B is based on raw data and the differences to baseline for each condom group.
 
The descriptive analysis of measure of Event-level Male Sexual (EMSEX) pleasure scale at the end of a 4-week assessment period and the difference to baseline for Test Condom A.
 
The descriptive analysis of measure of Event-level Male Sexual (EMSEX) pleasure scale at the end of a 4-week assessment period and the difference to baseline for Test Condom B.
 
The descriptive analysis of the proportion values of IELT increasement is based on the proportion of subjects who achieve an increase of 2 minutes on the IELT.
 
The descriptive analysis of the proportion values of IELT increasement is based on the proportion of subjects who achieve an increase of 3 minutes on the IELT.
 
The descriptive analysis of the proportion values of IELT increasement is based on the proportion of subjects who achieve an increase of 4 minutes on the IELT.
 
For all endpoints of 'subject perceived questionnaires' (SPQ) for subject the existing categories are counted for the descriptive analysis. The absolute numbers as well as the percentage distribution are shown. In addition, the upper two categories (strongly agree or agree) are counted together, i.e. the number and percentage of respondents who are in at least one of the two categories.
 
The descriptive analysis of the change in 'patient global impression' is based on each of the PGIC categories at 4 the end of the week.
 
For the endpoint 'User acceptability, experience and preference of each condom' for subject perceived questions at the end of 4 week assessment time is counted for the descriptive analysis.
 
The descriptive analysis of the in-use tolerability of each condom type will be evaluated for through subject perceived questions at each assessment time based on the safety data.
 
The descriptive analysis of a measure of the total clinical failure rate is based on the raw data for each condom group.

----------------------	--

95 % confidence intervals	
For the analysis of the IELT with the 5% Benzocaine condom versus the standard NRL condom, 95% confidence intervals and an associated p-value are calculated. The calculation is done for each estimator of each time point separately for each condom group.
 
For the proportion of subjects in the total collective who achieved increase of 2, 3, 4 mins, comparison between the 5% and 3% Benzocaine condoms with the standard NRL condom will be expressed as an odds ratio, with an associated 95% CI.
 
For the analysis of PGIC, the comparison between the 5% and 3% Benzocaine condoms with the standard NRL condom will be expressed as an odds ratio, with an associated 95% CI.
 
For the descriptive analysis of EMSEX pleasure scale the 95%-CI will be displayed.
 
95%-Hodges-Lehmann-CI in case a GLMM-approach fails.

---------------------------	--

Sensitivity analysis of selected secondary endpoints	
In case of a relevant discrepancy between the sample size of the FAS and the PP population, a sensitivity analysis will be performed on the per protocol (PP) population, which will include data from subjects being compliant with the protocol.
 
The following rule is applied:
 
If the sample sizes of the FAS and PP populations differ by at least 10%, the following endpoints will be analysed on the basis of the PP population.
 
 
1) Proportion of subjects who achieve an increase of 2 mins from baseline in IELT in the 3% benzocaine condoms compared to the standard NRL condom.
 
2) Proportion of subjects who achieve an increase of 3 mins from baseline in IELT in the 3% benzocaine condoms compared to the standard NRL condom.
 
3) Proportion of subjects who achieve an increase of 4 mins from baseline in IELT in the 3% benzocaine condoms compared to the standard NRL condom.
 
4) Proportion of subjects who achieve an increase of 2 mins from baseline in IELT in the 5% benzocaine condoms compared to the standard NRL condom.
 
5) Proportion of subjects who achieve an increase of 3 mins from baseline in IELT in the 5% benzocaine condoms compared to the standard NRL condom.
 
6) Proportion of subjects who achieve an increase of 4 mins from baseline in IELT in the 5% benzocaine condoms compared to the standard NRL condom.
 
 
Clinically relevant differences between the results of the FAS and the PP analysis are highlighted and discussed.

--	--

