## 8 Analysis Datasets

The analysis populations will be as follows:

- The safety population will include all randomised subjects who use at least one of the study condoms. The safety population will be used for all baseline summaries and summary of safety data. For the safety population, subjects will be analysed according to treatment received.
- The Full Analysis Set (FAS) will include all randomised subjects who use at least one of the study condoms and who have IELT recorded in at least one of the post-baseline study periods. The FAS will be used for the analysis of all efficacy endpoints. For the FAS, subjects will be analysed according to their randomised treatment.
- The Per Protocol (PP) population will consist of all subjects in the FAS who do not deviate from the protocol in such a way as to impact the evaluation of the primary endpoint. Subjects who do not have an IELT recorded for at least 4 condom uses within a treatment period will be excluded from the PP population for that period. All decisions on exclusions from the PP population will be made prior to database lock. For the PP population, subjects will be analysed according to treatment received.

The final assignment to the FAS and PP population is based on the data review meeting prior to database hardlock. The data review meeting committee is composed of different experts from the sponsor and the CRO.

The disposition of all subjects is shown using a flow chart including all screened subjects.

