### **IELT**

There will be no imputation for missing data. By using a mixed model, subjects who provide data for only one or two of the three assessment periods will be included in the FAS-analysis. For the calculation of mean IELT within an assessment period, only intercourse episodes where IELT is recorded will be included in the analysis.

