## Overview

The summary of the statistical analysis scheme is presented in the following table:

Target variables	Population	Graphs	Statistical methods
Disposition of subjects	SP	Flowchart	
Disposition of investigational products	SP	Flowchart	
Baseline characteristics	SP		
childbearing potential, ethnicity, physical examination	SP	--	Counts and percentages
Age, height, weight, BMI	SP	--	Descriptive statistics
Medical history	SP	--	Counts and percentages
Primary variable*	FAS*, PP**		
IELT with the 5% Benzocaine condom A		Bar chart	Descriptive statistics 95 % Confidence Intervals GLMM or Wilcoxon signed ranks test
Secondary variable(s)	FAS		
IELT with the 3% Benzocaine condom B	FAS**, PP**	Bar chart	Descriptive statistics 95 % Confidence Intervals GLMM or Wilcoxon signed ranks test
EMSEX Pleasure Scale for Test Condom A OR B against standard NRL condom	FAS**	--	Descriptive statistics 95 % Confidence Intervals GLMM or Wilcoxon signed ranks test
Patient Global Impression of Change (PGIC)	FAS**	--	Counts and percentages GLMM or Wilcoxon signed ranks test 95 % Confidence Intervals
Subject perceived questions	FAS**		Counts and percentages

Target variables	Population	Graphs	Statistical methods
Proportion of subjects who achieve an increase of 2 mins from baseline in IELT	FAS**, PP***	--	Descriptive statistics Counts and percentages GLMM or Wilcoxon signed ranks test 95 % Confidence Intervals
Proportion of subjects who achieve an increase of 3 mins from baseline in IELT	FAS**, PP***	--	
Proportion of subjects who achieve an increase of 4 mins from baseline in IELT	FAS**, PP***	--	
Total clinical failure rate	FAS**	--	Descriptive statistics Counts and percentages

\*: Confirmatory hypothesis testing

\*\*: No confirmatory hypothesis testing, part of secondary analysis

\*\*\*: Provided that the rule for sensitivity analysis from chapter 12.2 applies.

Additional tables and figures are acceptable for illustrative purposes. Additional statistical tests can be performed, if reasons are given in the final report. The corresponding p-values have to be interpreted purely descriptive in the context of an explorative data analysis.

Examples of crucial tables, listings and figures can be seen in Chapter 19.

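### The 10% trigger for the per-protocol responder analyses has no defined unit; counted in subjects, it can stay off while many short periods are excluded

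*SAP*

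**What the plan says.** Three rules in the SAP meet here.

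- **PP membership (section 8).** A man with fewer than four recorded times under one condom type "will be excluded from the PP population for that period". Exclusion for too few records therefore works period by period. Protocol section 9.3 has the same rule.
- **FAS membership (sections 8 and 10.6).** The FAS takes randomised condom users "who have IELT recorded in at least one of the post-baseline study periods". Section 10.6 adds that "subjects who provide data for only one or two of the three assessment periods will be included in the FAS-analysis".
- **The trigger (section 12.3, sensitivity analysis of selected secondary endpoints).** The PP analysis of the six responder comparisons runs on the condition "If the sample sizes of the FAS and PP populations differ by at least 10" per cent. The sentence before it describes the PP population as one "which will include data from subjects being compliant with the protocol". The unit of sample size is not defined.

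The topline list (section 17), the Overview and the notes to the planned tables all refer back to the trigger with the words "Provided that the rule for sensitivity analysis from chapter 12.2 applies". Section 12.2 holds the primary hypotheses; the rule stands in 12.3.

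**The concern.** Exclusion works by period, but the alarm appears to count people. A man with one or two short periods and one compliant period belongs to both sets, so his excluded periods do not change the head count. Under the four-record rule, a subject leaves PP altogether only if none of his periods complies.

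Short periods could plausibly collect in one condom type. The test products are desensitisers, and the IELT diary offers failure to ejaculate as a reason for having no recorded time (SAP 9.1). A subject may move on once he has four records (protocol 7.4). SAP 11.4 and table 19.6 then discard times affected by breakage or by slippage during intercourse and note that this can alter PP status, so one discarded value takes a four-record period down to three. A head count cannot detect a pattern confined to one condom.

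At stake is whether the six responder results, all listed for the topline, are checked against compliant data, and whether the FAS-versus-PP discussion promised in 12.3 takes place when the two data sets differ materially.

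**Working it through.** **Size of the trial.** Protocol 3.3 and SAP 12.7 give SD 7.1, correlation 0.5, difference 2 minutes, two-sided 5% and 90% power. SD of the paired difference = 7.1 × √(2 × (1 − 0.5)) = 7.1. The normal approximation gives 132.4, so 133; the noncentral t gives 135 (power 0.901). 135 / 0.9 = 150. The plan's 135 and 150 are reproduced. The 10% trigger is a rule with no derivation to check.

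**Setting.** Take N = 150 subjects with three periods each, 450 subject-periods. Assume every subject has some IELT data in every period and that the four-record rule is the only PP exclusion.

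**Counted in subjects, with no probability model.** The trigger needs 0.10 × 150 = 15 subjects with no compliant period.

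- Every subject has one short period: 150/450 = 33.3% of periods excluded; FAS 150, PP 150; difference 0%.
- Short periods in the 5% condom only, up to all 150 of them: each subject keeps two compliant periods; difference 0%.
- Every subject has two short periods: 300/450 = 66.7% excluded; difference 0%.
- Most that can be excluded without firing: 14 subjects lose three and 136 lose two, 14 × 3 + 136 × 2 = 314; 314/450 = 69.8%.
- With N = 135 the trigger needs 14 subjects, and the maximum is 13 × 3 + 122 × 2 = 283 of 405 = 69.9%.

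**Counted in subjects, with a model.** Let p be the probability that a period is short and ρ the within-subject correlation of shortness. Both are assumptions; the documents give neither. Under a beta-binomial model with s = 1/ρ − 1 and a = p·s, the probability of losing all three periods is π = a(a+1)(a+2) / [s(s+1)(s+2)], which becomes p³ for independent periods. The probability of firing is P(X ≥ 15) with X ~ Binomial(150, π). At p = 1/3:

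| ρ | π | P(trigger) |
|---|---|---|
| 0 | 3.7% | 0.0005 |
| 0.1 | 6.1% | 0.04 |
| 0.2 | 8.6% | 0.32 |
| 0.3 | 11.4% | 0.74 |
| 0.5 | 17.3% | 0.996 |

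For example, at ρ = 0.5: s = 1, a = 1/3, π = (1/3 × 4/3 × 7/3) / (1 × 2 × 3) = 0.173. With independent periods, the expected head-count difference reaches 10% only at p = 0.10^(1/3) = 46.4%. With complete clustering it does so at 15 × 3 = 45 of 450 periods, which is 10%.

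**Counted in periods.** The trigger fires at 0.10 × 450 = 45 periods, so it always fires when one third are short. If all the short periods fall in one condom, a pooled count still needs 45/150 = 30% of that condom's periods.

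**Which unit is meant.** For subjects: section 8 defines both sets as sets of subjects, the sentence before the trigger speaks of compliant subjects, planned Table 14.1.1 counts subjects per analysis set, and section 17 reports the allocation of subjects to populations. For periods: section 8 excludes by period, and the protocol synopsis describes the PP data by compliant treatment period. Subjects is the likelier reading, but the SAP does not settle it.

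**The case against.** The other side has good points, and several stand.

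- A reader might infer that the PP responder analyses will stay off whenever a third of periods are short. The documents do not support that. The unit is undefined, a period count fires at 10%, and even a head count probably fires at one third once ρ is about 0.3. Nor does the rule need perfect correlation to work. Some clustering is likely, since the same couple and diary habits recur in every period; among non-negative correlations, independence is the case least likely to fire.
- A reader might measure the gap by the share of subjects lacking a compliant pair of 5% and control periods. That answers another question: the responder model has a random subject effect and keeps subjects with one or two periods.
- A reader might count abandoned periods as part of the gap. A period with no IELT enters neither analysis, and one stopped after four valid records satisfies the four-record rule. Only periods with one to three valid IELTs, or with another PP deviation, separate the two sets. Deviations that remove whole subjects would help the head count reach 10%.
- High rates of short periods are not predicted by the plan. It requires regular intercourse and four baseline records, supplies eight condoms per type and reviews the diaries.
- A reader might infer that the primary result loses its PP check. Section 12.3 repeats the IELT change analysis in PP, and section 17 lists the primary endpoint in FAS and PP without the 10% condition. Section 12.3 does open with a separate condition about deviations that warrant exclusion from the FAS. The Overview and Tables 14.2.2.1 to 14.2.2.3 also give the 3% IELT change in PP without the trigger, although the topline heading in section 17 places it under the condition. Because the responder variables are cut-points of the same period means, a distortion in one condom should largely show in those tables.

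Gating a secondary sensitivity analysis is a legitimate choice. What remains is that this gate has no stated unit and, on its likelier reading, does not match the PP definition it is meant to monitor.

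**Conclusion.** The point holds in limited form. The trigger's unit is undefined. Counted in subjects, it shows a 0% difference with one short period per subject or with short periods confined to the 5% condom, and it can stay off with up to 314 of 450 periods excluded. Those counts assume N = 150, some IELT data in every period and no other PP exclusions. How often the trigger would fail depends on an unknown rate and clustering of short periods; at one third short, the probability of firing runs from 0.0005 to 0.996 as ρ goes from 0 to 0.5. The effect is confined to sensitivity analyses of non-confirmatory secondary endpoints. Severity is minor and confidence moderate, because the subject reading is likely but not stated. The references to chapter 12.2 are a certain but clerical error.

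**What to change.** In SAP 12.3, delete the 10% trigger and run the six responder comparisons on the PP set in all cases. If a trigger is preferred, define it as FAS periods minus PP periods of at least 10% of subject-periods for any one condom type. With 150 FAS periods per condom that is 15 periods, against the 45 that a pooled count would need. Change the references to chapter 12.2 in section 17, the Overview and the table notes to 12.3, and make clear in section 17 whether the condition covers the 3% IELT change.

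The cost is SAP wording, preferably before unblinding, and a few extra model runs and tables. The planned Tables 14.2.2.4 to 14.2.2.15 already provide for both FAS and PP.

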## 12.4 Considerations for non-inferiority and equivalence testing

Not applicable.

## 12.5 Model Assumptions

No assumptions of normality will be checked based upon the utilization of the Generalized Linear Mixed Model (GLMM) to analyze the primary endpoint. If the model can't handle the violation, then worst case scenario a non-parametric model will be used, such as Wilcoxon signed ranks test with Hodges Lehmann estimator for treatment differences.

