## 9.5 Statistical Analyses

All statistical analysis will be performed using SAS® version 9.4 or higher. For all endpoints, in the event that the assumptions underlying the parametric approach are violated, alternative non-parametric methods will be used.

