### 10.2 Unblinding

Unblinding will take place after locking of the final database. It will be performed in SAS® by combining the imported randomisation list and each SAS® table containing relevant information for the trial. Randomisation numbers are used to match files correctly. The corresponding code will be filed.

Blinded and unblinded data will be listed separately.

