**For primary endpoint:**

The primary endpoint of the investigation is the change from baseline in IELT with the 5% Benzocaine condom versus the standard NRL condom, over a 4-week assessment period. For each subject, a mean IELT will be calculated across all intercourse episodes within a study period (baseline, assessment period 1, assessment period 2 and assessment period 3) and used for analysis.

For the calculation of the respective mean values, only IELT data points that were generated during a condom-based clinical-failure-free sexual intercourse are taken into account. Ejaculation is to be considered the posterior threshold.

If an IELT value is not considered valid due to the regulation listed in table 19.6 located in the appendix, it is not used in the calculation and is formally considered non-existent in the primary and secondary analyses. This value is also not considered further in any descriptive analysis.

Consequently, the classification of some values as "non-valid" can affect the categorization of the FAS and PP analysis population, as excluded IELT values cannot be evaluated in this consideration either.

The change from baseline in IELT will be analysed using a linear mixed model using data from all three condom groups, with the primary comparison between the 5% benzocaine condom with the standard NRL condom. The model will include fixed effects for treatment and period, a covariate for baseline IELT, and a subject as a random effect. The differences between the 5% benzocaine condom and the standard NRL condom will be presented with a 95% CI and an associated p-value. Statistical significance will be assessed at the two-sided 5% level. No adjustment for multiplicity will be made since there is a single primary comparison (5% benzocaine condom versus standard NRL condom). No assumptions of normality will be checked based on utilizing the Generalized Linear Mixed Model (GLMM) to analyze the primary endpoint. If the model can't handle the violation, a non-parametric model will be used in the worst-case scenario, such as Wilcoxon signed ranks test with Hodges Lehmann estimator for treatment differences.

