## 12.7 Sample size and statistical power

In a publication titled "A Multinational Population Survey of Intravaginal Ejaculation Latency Time (Waldinger et al., 2005)", 500 couples were studied in a non-interventional setting over a 4-week period. The mean IELT was 8 minutes (SD = 7.1). Assuming this will be representative of the IELT of men using the standard NRL condom, and that the correlation between repeated measurements within the same subject in the 3 periods of the crossover trial will be 0.5, the table below shows the number of subjects required to detect a clinically meaningful difference of 2 minutes in mean IELT between the Test Condom A (5% Benzocaine paste) and the Control NRL Condom at 90% power, with a significance level of 5% using a two-sided paired t-test.

IELT (mins)		Number of Subjects	
Control NRL Condom	Test Condom A (5% Benzocaine paste)	Number to complete	Number randomised (10% drop out)
8	10	135	150

A sample size of 135 subjects will be sufficient to detect a difference of 2 minutes in mean IELT between the Test Condom A and the Control NRL Condom. Allowing for a dropout rate of 10%, 150 subjects will be randomized.

A 2 minute difference in IELT is considered clinically meaningful based on previous studies identified in the published literature. Shabsigh et al (2019) conducted a randomised controlled trial of topical 4% benzocaine wipes for the management of PE defined as self-reported poor control over ejaculation and an IELT of 2 minutes or less. Results showed a statistically significant increase in mean IELT of 164.80 ( $\pm 11.40$  SE) seconds after 1 month of treatment compared to placebo (110.10 s  $\pm 9.90$  SE). The clinical benefit of a difference in IELT of 1 minute or larger compared to placebo is demonstrated via a patient reported outcome known as the Index of Premature Ejaculation (IPE) whereby the men in the treatment group reported significantly higher sexual satisfaction and greater improvement in distress related to intercourse. For the purposes of relevance to the target population, a larger 2-minute difference in IELT has been selected as the relevant effect for this clinical investigation based on the subjects being healthy adult men as opposed to only men with PE (IELT <2 minutes).

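### The primary test has a rank-test fallback with no trigger: the plan declines to check normality, yet would change both method and target quantity on a violation

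*SAP*

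**What the plan says.** **The model.** SAP section 11.4 and Protocol section 9.5.1.1 specify a linear mixed model for change from baseline in IELT, with treatment, period, baseline IELT and a random subject effect. "Statistical significance will be assessed at the two-sided 5% level" (SAP 11.4). SAP 12.1 relabels this a generalized linear mixed model but writes it as a linear predictor with normal random effects. It names no non-normal distribution and no link.

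**The check.** SAP 12.5: "No assumptions of normality will be checked based upon the utilization of the Generalized Linear Mixed Model (GLMM) to analyze the primary endpoint". Protocol 9.5.1.1 and SAP 11.4 carry essentially the same sentence.

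**The fallback.** SAP 12.5 continues: "If the model can't handle the violation, then worst case scenario a non-parametric model will be used, such as Wilcoxon signed ranks test". SAP 12.2 repeats it, SAP 12.3 adds a Hodges-Lehmann interval should the GLMM approach fail, and the SAP Overview table lists GLMM or Wilcoxon for the primary variable.

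**The other rule.** Protocol 9.5, for all endpoints: "in the event that the assumptions underlying the parametric approach are violated, alternative non-parametric methods will be used". The synopsis says the same of the model assumptions.

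**Timing.** SAP 10.2: "Unblinding will take place after locking of the final database". The data review before lock (SAP 8) is described only for assigning the FAS and PP populations.

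**A second switch.** SAP 12.1 starts from compound symmetry: "If this model doesn't fit, an unstructured covariance can be used instead".

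**The concern.** This is the trial's only confirmatory test. SAP 12.6 justifies the lack of multiplicity adjustment by there being a single primary comparison, and that argument needs a single test as well.

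Two rules conflict. One switches method when assumptions fail; the other declines to look at normality but still switches on an undefined violation. The conflict begins inside the protocol (synopsis and 9.5 against 9.5.1.1), and the SAP inherits it. The stated reason for not checking does not work either: calling the model a GLMM does not remove the normal-error assumption from a linear mixed model.

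The switch also changes the question. Protocol 2.2 states success on mean IELT, and the sample size is the "number of subjects required to detect a clinically meaningful difference of 2 minutes in mean IELT" (SAP 12.7). SAP 12.12 describes the fallback interval as one for the median difference. A paired signed-rank test has no period or baseline term. Baseline is constant within a man and cancels from his difference; period does not. The test also drops men lacking either the Test Condom A or the control period, whom SAP 10.6 keeps.

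**Working it through.** **1. The plan's sample size.** Inputs from SAP 12.7: SD 7.1, correlation 0.5, difference 2 minutes, "90% power, with a significance level of 5% using a two-sided paired t-test".

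- SD of the paired difference = 7.1 × √(2 × (1 − 0.5)) = 7.1.
- Normal approximation: ((1.960 + 1.282) × 7.1 / 2)² = 132.4, so 133.
- Noncentral t: the smallest n with at least 90% power is 135 (power 0.901).
- 135 / 0.90 = 150 randomised.

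The stated 135 and 150 reproduce, and they rest on a test of means.

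**2. Assumed distribution.** The documents give a mean and SD but no shape. An SD of 7.1 on a mean of 8 for a positive variable makes right skew plausible, so log-normal IELT is assumed.

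- Log-scale SD = √ln(1 + (7.1/8)²) = 0.762.
- Log-scale correlation = ln(1 + 0.5 × (7.1/8)²) / 0.762² = 0.572, which gives 0.5 on the raw scale.

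**3. Simulation.** 20,000 trials per row with 135 pairs, using a paired t-test as a stand-in for the mixed-model contrast. The last column is the population value that Hodges-Lehmann estimates, from 4 million draws.

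| Scenario | Mean gain | t-test significant | Wilcoxon significant | Either significant | Disagree | Hodges-Lehmann target |
|---|---|---|---|---|---|---|
| No effect | 0 | 4.7% | 5.0% | 7.1% | 4.5% | 0.0 |
| Constant shift of 2 min | 2.0 | 89.6% | 99.6% | 99.6% | 10.0% | 2.0 |
| Proportional, ×1.25 | 2.0 | 84.0% | 91.8% | 93.3% | 10.8% | 1.5 |
| 25% of men gain 8 min | 2.0 | 83.6% | 90.9% | 92.5% | 10.5% | 1.8 |
| 50% of men gain 4 min | 2.0 | 87.8% | 98.7% | 98.7% | 10.9% | 2.0 |

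A null run of 80,000 trials gave 4.7%, 4.9% and 7.1%. With normal differences instead, the null figures are 5.0%, 5.0% and 6.0%.

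**4. Fitting the linear or mixed model instead of the t-test.** Null rejection was 4.0 to 4.8% for the model, 4.3 to 5.1% for Wilcoxon, and 6.2 to 7.5% for either. In the proportional scenario the model estimate averaged 2.0 minutes against 1.5 for Hodges-Lehmann. The chance of an estimate of at least 2 minutes was 50 to 51% against 14 to 15%. Under a constant shift it was 50% against 51%.

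**The case against.** The best defence is that the plan names a default model with its terms and describes the rank test as a last resort. Nothing permits taking the smaller p-value. A switch driven only by non-normal residuals was simulated under the same log-normal inputs (10,000 null trials). A Shapiro-Wilk test rejected normality every time, and the error of the whole procedure was 5.0%. That stands: inflation needs a choice driven by the results.

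It also stands that not checking normality does no harm if the mixed model is kept regardless, since its error rate holds at this size. The gap between the two estimates depends on the shape of the effect and vanishes under a constant shift. The two-minute threshold binds the estimate only on the wording of Protocol 2.2; the synopsis asks for p < 0.05 and calls two minutes clinically meaningful.

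Protocol 9.1 requires departures from the planned analysis to be documented before database lock. This helps less than it seems: the fallback is already part of the plan, so invoking it need not count as a departure.

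None of this supplies a trigger or reconciles the two rules.

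**Conclusion.** The concern holds as a defect of specification in the one confirmatory analysis. The rules conflict, the stated reason is wrong, and no trigger, decision-maker or timing is given.

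Its size rests on the log-normal assumption in step 2. Each test alone holds about 4 to 5% error, and about 6 to 7.5% is a worst case. At a true mean gain of 2 minutes, Hodges-Lehmann targets about 1.5 to 2.0 minutes depending on the form of the effect. Across runs the two tests disagree on significance in about 9 to 11% of such trials.

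A reader might infer more than the documents support:

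- That type I error control is broken. This needs selection on the result, which no passage allows.
- That the choice will be made on unblinded data. The documents merely fail to prevent it.
- That normality is untestable. Residuals could be examined; the plan declines to do so.
- That compound symmetry is the wrong default. No evidence shows this, and it held its level in simulation. Only the undefined switch away from it is at fault.

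**What to change.** 1. Make the linear mixed model (treatment, period, baseline IELT, random subject) the sole primary analysis, whatever the residuals look like.
2. Report Wilcoxon with Hodges-Lehmann only as a named sensitivity analysis that cannot replace it.
3. Keep compound symmetry as the default, and replace the loose condition in SAP 12.1 with an objective, pre-specified trigger such as non-convergence.
4. Delete the sentence that declines the normality check because of the GLMM label.
5. Align the protocol synopsis, 9.5 and 9.5.1.1 with SAP 11.4, 12.1, 12.2, 12.3, 12.5 and the Overview table, before database lock.

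The cost is a SAP amendment and a protocol clarification; the sample size stays at 135 and 150. The sponsor gives up the option of moving to the rank test, which is more powerful under skew (about 92% against 84% in the proportional scenario) but estimates a different quantity whenever the paired differences are asymmetric.
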